### **5.1.1 Dosing schedule for intensive and population PK studies**

Of note, in malaria studies, it is standard practice to refer to the 1st day of treatment as study day 0. This nomenclature is used universally in the clinical care of malaria patients, and has been the standard for all our studies in Uganda. We will use the study day nomenclature throughout this protocol.

The primary focus of the **intensive PK studies** involves PK sampling around the last dose of the AL regimen. To ensure that we can begin intensive sampling around the last dose or AL, a modest alteration in the dosing schedule will be made so that the last dose falls in morning. This alteration does not affect treatment efficacy or safety and we have used this approach for our prior intensive PK studies of AL. The dosing schedule specified in Table 4 will be used to assure a) adequate AL treatment and b) the scheduling of intensive PK sampling during the day, rather than during the night.

- AL treatment for the 3-day regimen will be 6 doses of Coartem® administered over 4 days (Study Days 0, 1, 2 and 3) as per weight-based dosing guidelines. Sampling will begin in the morning of day 3. The 6-dose regimen is the standard of care for the treatment of malaria

- AL treatment for the 5-day regimen will be 10 doses of Coartem® administered over 6 days (Study Days 0, 1, 2, 3, 4, and 5) as per weight-based dosing guidelines. Sampling will begin in the morning of day 5.
- Children will be presenting for care at various times of the day. Therefore, the precise timing of the 1st and 2nd dose on Day 0 will be left to the discretion of the medical officer.
- However, spacing between the 1st and 2nd doses of AL should be a minimum of 7 hours and maximum of 10 hours.

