#### 9.4.2 Intensive PK Analysis

PK parameters for each subject will be estimated using non-compartmental analysis (NONCMP) and follow a linear up-log down trapezoidal rule in conjunction with first-order input (WinNonlin). PK parameters, including the elimination rate constant  $\lambda_z$  and  $t_{1/2}$  will be estimated, with  $t_{1/2}$  calculated as  $\ln_2/\lambda_z$ . AUC will be estimated as the  $AUC_{0-8h}$  or  $AUC_{0-24h}$  (as results permit) for artemether/DHA and the sum of  $AUC_{last}$  (AUC to the

end of the sampling period) and  $AUC_{last-\infty}$  (from the end of sampling to infinity) for lumefantrine/ desbutyl-lumefantrine. PK parameters will be compared between groups of interest (Figure 1 and Table 8) using a two-sided unpaired t-test for two-group comparisons, and ANOVA for multi-group comparisons. If PK parameters are found to have skewed distributions and data transformations do not induce symmetry, rank-based tests will be used. To enhance comparison between 3-day and 5-day AL, peak concentrations collected on Days 0-4 will be integrated using population methods. The following groups will be compared:

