### 9.5.2 Population PK Analysis and Correlation of AL PK with treatment outcomes.

Population PK analysis will utilize both intensive and sparse PK sampling data for both HIV infected and HIV uninfected children. Plasma concentrations will be transformed

into natural logarithms and concentration-time profiles will be analyzed using non-linear mixed effects (NLME). For NLME modeling, PK data will be analyzed using a standard PK model formalism. To analyze population data the PK model is embedded in a two-stage NLME model, accounting for both intra- and inter-subject variability. The estimation of NLME parameters will be accomplished using the software NONMEM (version 7; Icon Development Solutions, Maryland), in particular the first order conditional estimation method with interaction that uses a linear approximation to the likelihood of the data. Diagnostic graphics and post-processing of NONMEM output and simulations will be performed using the statistical software R. Model development will be guided by exploratory analysis of the data, changes in the NONMEM objective function value, and diagnostic plots. Our recent lumefantrine modeling suggest a two- and three-compartment model provide the best fit, respectively, though additional models will be tested Alternative models for intra-subject variability (proportional and constant plus proportional) will be explored as appropriate. To reinforce the primary objectives, base model building will also include quantification and formal test of the impact of EFV on PK of AL. Specifically, the impact of HIV treatment will be tested as potential covariate on clearance and/or bioavailability. Further stepwise covariate analysis will be performed to identify the impact of covariates on the PK of AL with special focus on the impact of markers of malnutrition, as measured by weight, BMI, and various Z scores and mid-arm circumference. Other covariates will include age, body size (weight, height), concomitant medications, parasitemia, hematocrit, and CD4 count (for HIV-infected children). Both linear and nonlinear relationship between continuous covariates and model parameters will be investigated in a stepwise fashion. Subject-specific estimates of artemether, DHA, lumefantrine, and desbutyl-LR exposure will be obtained from individual PK analyses for subjects with intensive PK sampling (AUC) and a posteriori from population PK analysis (as given by dose/(CL/F)). These estimates will be used to test for a significant relationship between drug exposure and the primary treatment outcome (recurrent infection at day 28-42 using standard WHO treatment outcomes) using Cox proportional hazard models with robust sandwich estimators that account for correlated data, as individuals may be enrolled for multiple episodes of malaria. A secondary outcome will be sub-patent infections detectable by LAMP, which will also be analyzed for associations with PK exposure using Cox models. Simultaneous PK/PD analysis will be performed to maximize the entire database. As for PK, we will investigate if there is any potential impact of indices of malnutrition, HIV status, age and other covariates on PD parameters. In other words, we will identify if target concentrations to prevent reinfection might be altered in different patient population due to known covariates. Once targets are identified, population PK models will be used to simulate different AL PK dosing approaches to identify optimized regimens that ensure concentrations are maintained within the concentration range necessary to maximize efficacy in all studied populations.

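### Section 9.5.2 names two non-equivalent exposure measures for the Cox recurrence analysis, leaves the dose in one of them undefined, and gives no rule for a common scale

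*Combined protocol and SAP*

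**What the plan says.** Section 9.5.2 lists two sources of exposure in one sentence. Estimates "will be obtained from individual PK analyses for subjects with intensive PK sampling (AUC) and a posteriori from population PK analysis", the latter "as given by dose/(CL/F"). The next sentence sends both to the outcome model: "These estimates will be used to test for a significant relationship between drug exposure and the primary treatment outcome", by Cox models with robust standard errors. Recurrent malaria by day 42 is a primary outcome in 9.2.1.

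Section 9.4.2 defines the individual analysis: "PK parameters for each subject will be estimated using non-compartmental analysis (NONCMP"). For artemether and DHA the AUC covers 8 or 24 hours. For lumefantrine it is the AUC to the last sample plus extrapolation to infinity. Section 5.1.1 says that the intensive study "involves PK sampling around the last dose of the AL regimen". Section 6.7.1 and Appendix A agree: rich venous sampling surrounds the 6th or 10th dose, and the later nominal times in Appendix A (24, 120, 288 and 456 hours) are set relative to that dose.

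Nowhere do the documents say whether the dose in dose/(CL/F) is one dose or the whole course. Nor do they adjust the Cox model for sub-study or say which estimate is used when a child has both.

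**The concern.** A lumefantrine AUC that starts at the last dose includes carry-over but leaves out most of the exposure already accrued from the earlier doses. Dose/(CL/F) is either the AUC of one dose or the AUC of the full 6 or 10 doses. For lumefantrine the last-dose AUC equals neither.

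If both enter the Cox analysis as exposure, two children with the same clearance and regimen get different values because they were in different sub-studies. Sub-study is not randomised: under 3.1.2 and 3.2.3 children preferentially take part in the intensive study first, so the measure would also be tied to episode order. What is at stake is the slope of recurrence on lumefantrine exposure, which is how the plan links the pharmacokinetics to a primary outcome. If both estimates exist for intensive children, the choice between them is left until the data are in hand.

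**Working it through.** **The plan's own figure.** Section 9.5.1 anticipates a 1.7-fold AUC increase from 3-day to 5-day treatment and gives no derivation. The ratio of doses is 10/6 = 1.67, which rounds to 1.7. The figure is therefore what whole-course dose/(CL/F) gives at equal CL/F.

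**Inputs from the protocol.**
- Lumefantrine half-life (Table 1): 23.7 h with efavirenz (21.8, 46.0); 64.3 h in uninfected children (52.0, 121).
- Dose times (Table 4, mid-window, hours from midnight of day 0): 14, 23, 38, 57, 69, 81 for 3-day; then 93, 105, 117, 129 for 5-day.
- AUC CV: 35-38% (9.4.1).
- Planned numbers (3.2): intensive 60 of 160 HIV-infected and 100 of 220 uninfected.

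**Assumptions.** One-compartment linear kinetics; the same clearance in both sub-studies; absorption either instantaneous or first-order with ka 0.15-0.6/h.

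**Formula.** In units of one-dose AUC to infinity, with k = ln 2 / half-life and instantaneous absorption, the AUC from the last dose onward is the sum over doses of exp(-k(t_last - t_i)). The whole-course AUC is 6 or 10.

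**Worked case: efavirenz, 3-day, k = 0.0292/h.** 0.141 + 0.183 + 0.284 + 0.496 + 0.704 + 1 = 2.81. Whole course over last-dose AUC = 6/2.81 = 2.14.

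| Group (instantaneous absorption) | Last-dose AUC, 3-day | Last-dose AUC, 5-day | Whole course / last-dose, 3-day | Same, 5-day | 5-day/3-day ratio of last-dose AUC |
|---|---|---|---|---|---|
| Efavirenz | 2.81 | 3.24 | 2.14 | 3.09 | 1.15 |
| Uninfected | 4.30 | 5.89 | 1.40 | 1.70 | 1.37 |

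With ka = 0.15/h the multiples fall to 1.88 and 2.68 (efavirenz) and 1.32 and 1.60 (uninfected). This gives the overall ranges 1.9-3.1 and 1.3-1.7.

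**Sensitivity.**
- Half-life limits in Table 1, instantaneous absorption: multiples 1.56-3.28 (efavirenz) and 1.20-1.88 (uninfected); 5-day/3-day ratio of last-dose AUC 1.14-1.30 and 1.32-1.49.
- Very slow absorption (ka 0.05/h): multiples 1.55 and 2.13 (efavirenz), 1.22 and 1.45 (uninfected); ratios 1.22 and 1.41.

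No case brings the two measures together, and none brings the ratio to 1.67.

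**Share of episodes on the last-dose measure.** 60/160 = 37.5%; 100/220 = 45%; overall 160/380 = 42%.

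**Illustration of the slope.** I drew clearance as log-normal with log-SD 0.36, used the planned numbers per arm, gave intensive children the last-dose AUC and the others whole-course dose/(CL/F), and regressed true log whole-course exposure on this mixed variable. With instantaneous absorption the coefficient, which is the factor by which a log-exposure slope shrinks, is about 0.45-0.46 on efavirenz and 0.73-0.82 in uninfected children. The spread reflects whether half-life varies with clearance or is held fixed.

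**The case against.** The strongest reply is that the text is under-specified rather than wrong. Only the first clause is limited to intensively sampled children; the population clause has no such limit. Section 9.5.2 opens by fitting the population model to intensive and sparse data together, so every child will have a posterior estimate, and the section speaks of Cox models in the plural. Using the posterior estimate throughout would fit the wording. This stands: a reader might infer a firm plan to enter both measures as one variable, and the documents do not say so. They also do not say the opposite, and the natural reading sends both sets of estimates to the same test.

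The start of the lumefantrine AUC is likewise inferred from the sampling scheme. Intensive children also give samples from day 0, and 9.4.2 integrates the day 0-4 peaks by population methods, but only to support the 3-day versus 5-day comparison.

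A reader might also infer a discrepancy of up to about 6-fold and a posterior measure that carries no regimen difference. Both need the dose to mean a single dose. The 1.7-fold figure in 9.5.1 matches 10/6 and favours the whole-course reading.

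The figures are for lumefantrine under one-compartment kinetics, while 9.5.2 expects two or three compartments and 1.1.8 describes dose-limited absorption; the exact multiples would move. They do not carry over to artemether and DHA. With an assumed half-life of 1-3 h, the 8-hour AUC is 90-100% of a one-dose AUC, so the measures nearly agree on the one-dose reading and differ 6-fold or more on the whole-course reading.

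**Conclusion.** The point holds as a gap with a material consequence. Section 9.5.2 names two lumefantrine measures that differ whichever way the dose is read, and supplies no rule for a common one. On the whole-course reading the gap is about 1.9 to 3.1 times on efavirenz and 1.3 to 1.7 times in uninfected children. That is comparable with, or larger than, the 1.7-fold regimen difference the analysis hopes to exploit. Pooling would attenuate the exposure-recurrence slope, to roughly half on efavirenz in the illustration. The size depends on the kinetic assumptions above; the non-equivalence does not.

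The reach is limited. The AUC comparisons in 9.4.2 use intensive data only, and the randomised recurrence comparison between regimens uses no exposure measure, so neither is affected. A reader might infer that the target concentrations used to simulate dosing are distorted too. The documents do not support that: in 9.5.2 the targets follow from the simultaneous PK/PD analysis and are not said to come from the Cox slope.

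**What to change.** In 9.5.2, state that one model-based exposure measure will be used in the Cox analysis for every episode, intensive and sparse, taken from the joint population model. Whole-course AUC = total dose given/(CL/F), with the dose so defined, is one suitable choice. Add a model-predicted lumefantrine concentration at a fixed time as a sensitivity analysis. This is useful because whole-course AUC puts a ratio near 10/6 between regimens into the predictor almost by construction. Keep the non-compartmental AUC for the group comparisons in 9.4.2.

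The cost is a sentence or two in the analysis plan. The joint model is already planned, and no further samples or children are needed.

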#### HYPOTHESES:

- 1) 5-day AL will provide superior PK exposure and improved treatment outcomes compared to 3-day AL in HIV-infected EFV-treated children
- 2) 5-day AL in HIV-infected EFV-treated children will provide comparable PK exposure and outcomes to 3-day AL in HIV-uninfected children.
- 3) 5-day AL in HIV-uninfected children will provide superior PK exposure and improved treatment outcomes as compared to 3-day AL in HIV-uninfected children.

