### **3.2.3 All children**

- If a child has multiple episodes of malaria, they will be randomized for each episode into a 3-day or 5-day regimen. For example, a child could be randomized to a 3-day regimen for episode #1 and then randomized to either a 3-day or 5-day regimen for episode #2, or vice-versa.
- All sample sizes refer to “evaluable” PK participants, in other words, those that have completed follow-up sufficiently to obtain all required PK study samples (see Note\*).
- If a child does not complete PK sampling procedures for the intensive study for any reason (they are not “evaluable”), the child may be re-enrolled in the intensive PK study for subsequent episode(s) of malaria, if they meet eligibility requirements.
- All children can be enrolled into the intensive study for a maximum of two “evaluable” episodes of malaria.
  - \*Note: Up to 2 PK samples can be missing to still be considered “evaluable” for intensive PK. More than 2 missing PK samples will permit a child to either repeat a specific intensive study for a subsequent episode or be replaced. They may also be eligible to transition from the intensive study into the population PK sampling study, provided enrolment criteria are met. For any malaria episodes beyond the 4th episode, a child will be referred to the local health center for management.
- At least 28 days must separate each PK study malaria episode.
- All children will preferentially undergo intensive PK studies until the maximum of two episodes in the intensive sampling scheme has been reached

- A child may be enrolled for a maximum of 4 episodes of malaria over the study period whether deemed “evaluable” or not. For any malaria episodes beyond the 4th episode, a child will be referred to the local health center for management.
- If participation in the intensive study is not feasible for any reason or if the desired intensive sampling size has not been achieved, a child can be directly enrolled into the population studies.

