### 9.2 Outcome Measures

#### 9.2.1 Primary outcomes

- 1) Area under the plasma concentration versus time curve for all drug analytes.
- 2) Recurrent malaria following treatment by day 42 (recrudescence or new infection)

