## 9.5 Population PK study

### 9.5.1 Sample Size

160 episodes of malaria in HIV-infected children and 220 episodes of malaria in HIV-uninfected children (up to 4 episodes per child including up to 2 involving intensive sampling) are more than sufficient to obtain population PK parameter estimates for both groups of children with good precision. Outcomes will be assessed in children in both the intensive and population PK studies, as such, sample sizes reflect the sum of children enrolled in each arm for each type of PK sampling. Thus, total sample sizes will be 80 to 110 children per arm. Using WinPOPT®, the standard errors (SE) of all population PK parameters, including variability parameters, will be <20% of their means, except for the interindividual variability of  $k_a$ , for which the SE is estimated to be 32% of its mean. Based on our recent study from Tororo, where a 42-day recurrence rate of 47% was observed in those on EFV-based ART, we will have 80% power to detect a 20% difference in recurrence rates between 3-day and 5-day arms. Notably, in our previous exposure-outcomes, with 50 to 70 children in each ART arm and 184 children not on ART, a 2.1-fold change in AUC between those on EFV and lopinavir/ritonavir translated to a 2.7-fold increase in risk for reinfection. In other words, the anticipated increase in AUC between 5-day and 3-day AL of 1.7-fold increase in exposure is expected to translate to a clinically relevant change in risk in a similar number of subjects.

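### The only analysis written for the primary recurrence outcome is a Cox model on individual drug exposure, so recurrence is never compared between 5-day and 3-day AL as randomised

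*Combined protocol and SAP*

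**What the plan says.** - **Outcome.** Section 9.2.1 lists two primary outcomes: AUC for all analytes, and recurrent malaria by day 42, counting both recrudescent and new infections.
- **Hypothesis.** The schema states that "5-day AL will provide superior PK exposure and improved treatment outcomes compared to 3-day AL in HIV-infected EFV-treated children". Hypothesis 3 makes the same claim for HIV-uninfected children.
- **What is randomised.** Under Section 3.2.3, if children have several malaria episodes, "they will be randomized for each episode into a 3-day or 5-day regimen".
- **Power.** Section 9.5.1 takes a 47% recurrence rate on EFV-based ART and says "we will have 80% power to detect a 20% difference in recurrence rates between 3-day and 5-day arms". It counts intensive and population PK children together, giving 80 to 110 per arm.
- **Analysis of recurrence.** Section 9.5.2 takes each child's exposure estimate (AUC from intensive sampling, or dose/(CL/F) from the population model) and uses it to "test for a significant relationship between drug exposure and the primary treatment outcome", "using Cox proportional hazard models with robust sandwich estimators that account for correlated data". It adds PK/PD modelling that will look for "any potential impact of indices of malnutrition, HIV status, age and other covariates on PD parameters". Regimen is not named in either model.
- **Analysis by regimen.** Section 9.4.2 and Table 8 compare the regimens, by t-test, ANOVA or rank test, on PK parameters only. Section 6.4.6 classifies 28-day and 42-day treatment outcomes but gives no test.

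**The concern.** Randomisation protects one contrast, 5-day against 3-day. It does not protect a comparison of children with high and low drug exposure. The protocol itself names causes of exposure other than regimen: EFV, age and underweight (Sections 1.1.4, 1.1.6 and 1.1.7). The table in Section 1.1.9 lists EFV and underweight as raising reinfection risk as well. Section 1.1.3 notes that HIV-infected children use trimethoprim-sulfamethoxazole, so the HIV groups differ in more than drug exposure. An association between exposure and recurrence can arise from any of these.

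Two features of the exposure analysis add to this:

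- **Exposure measure.** Section 9.5.2 does not say whether the dose in dose/(CL/F) is a single dose or the whole course. If it is a single dose, the difference between regimens drops out of the exposure variable for children with sparse sampling.
- **Who is included.** PK sampling stops after treatment failure before Day 3 (Section 6.4.6) and after early failure (Section 6.7.1), and sample sizes count evaluable PK participants (Section 3.2.3). Whether an episode has a usable exposure estimate may therefore depend on its outcome.

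At stake is the answer to hypotheses 1 and 3. Followed literally, the trial could report that exposure predicts recurrence without a stated test of whether the longer regimen reduces it.

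**Working it through.** **Step 1. The plan's own figure for recurrence.** The inputs are 47% recurrence (Section 9.5.1) and 80 episodes per arm in HIV-infected children (Section 3.2). I assume that the 20% is an absolute difference and that alpha is 0.05 two-sided; the plan states neither for recurrence.

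- Mean risk = (0.47 + 0.27)/2 = 0.37.
- Null SE = √(2 × 0.37 × 0.63/80) = 0.0763.
- Alternative SE = √((0.47 × 0.53 + 0.27 × 0.73)/80) = 0.0747.
- Power = Φ[(0.20 − 1.96 × 0.0763)/0.0747] = Φ(0.67) = 75.0%.

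For a Cox test by arm, HR = ln(0.73)/ln(0.53) = 0.496 and events = 80 × (0.47 + 0.27) = 59.2. Schoenfeld power = Φ[(√59.2/2) × |ln 0.496| − 1.96] = Φ(0.74) = 77.0%.

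So the stated 80% recomputes to 75-77%, before any allowance for repeat episodes in one child. That shortfall is a separate and smaller matter. What counts here is that the figure is for a between-arm test, and no such test appears in Section 9.5.2.

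**Step 2. How much of the exposure variation is randomised.** Take AUC as log-normal, allocation as 1:1 and the regimen effect as the plan's 1.7-fold (Section 9.5.1).

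- Variance of log-AUC due to regimen = (ln 1.7/2)² = (0.5306/2)² = 0.0704.
- Variance between children on the same regimen = ln(1 + CV²).
- Regimen's share = 0.0704/(0.0704 + between-child variance).

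*On the planning CV (Section 9.4.1), within one HIV stratum:*

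- CV 35%: ln(1.1225) = 0.1156; share = 0.0704/0.1860 = 37.9%.
- CV 38%: ln(1.1444) = 0.1349; share = 0.0704/0.2053 = 34.3%.

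*On the spread in Table 1 (Section 1.1.4).* The log SD can be recovered from the lumefantrine AUC intervals as ln(upper/lower)/(2 × multiplier) × √n.

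- HIV-uninfected, 232 to 313, n=52: ln(313/232) = 0.2995. This gives 0.55 with multiplier 1.96 and 0.54 with the t value 2.01.
- HIV-infected on EFV, 107 to 157, n=31: ln(157/107) = 0.3834. This gives 0.54 with multiplier 1.96 and 0.52 with the t value 2.04.
- With log SD 0.53: share = 0.0704/(0.0704 + 0.2809) = 20.0%. This SD corresponds to a CV of √(e^0.2809 − 1) = 57%, well above the planning value.

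The part not randomised is therefore about 62% (100 − 37.9) to 80% (100 − 20.0).

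**Step 3. If both HIV strata enter one model.** Section 9.5.2 pools the HIV groups for the population PK model and does not say whether the Cox model is stratified. Use the EFV/control lumefantrine ratio of 0.48 (Table 1) and planned totals of 160 and 220.

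- Variance due to HIV/EFV status = (160/380) × (220/380) × (ln 0.48)² = 0.2438 × 0.5387 = 0.1313.
- CV 35%: total = 0.0704 + 0.1313 + 0.1156 = 0.3173; regimen 22%, HIV/EFV status 41%.
- CV 38%: total = 0.0704 + 0.1313 + 0.1349 = 0.3366; regimen 21%, HIV/EFV status 39%.

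In a pooled model, the non-randomised HIV/EFV contrast would contribute more to exposure than the randomised regimen does.

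**The case against.** The strongest reply is that this is a missing sentence and not a chosen method. Section 9.5.1 powers a recurrence difference between arms, so a by-arm comparison was plainly intended. Section 9.5.2 is headed as a correlation of PK with outcomes, and its content fits that heading. Exposure-response is also a declared aim: Section 9.1 says the study will examine the impact of AL exposure on treatment outcomes, and primary objective 4 concerns pharmacodynamics. Child-level correlation is already handled by the sandwich estimator and by the repeated-measures statement in Section 9.4.1. Malnutrition, HIV status and age will be examined in the PD modelling.

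Most of this stands, and it limits the point. It does not remove it. A power sentence gives no model, analysis set, alpha or treatment of repeat episodes, and these should not be left open for a primary outcome in an open-label trial. Covariates examined on PD parameters are not said to enter the Cox model, and adjusting for them would not replace randomisation.

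Three stronger readings are tempting but unsupported:

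- A reader might infer that nothing is compared as randomised. Section 9.4.2 and Table 8 do compare AUC between regimens in both HIV groups.
- A reader might infer that the sponsor decided to substitute exposure for the randomised comparison. Section 9.5.1 points the other way.
- A reader might take 62-80% as the size of the bias. It is a share of variance in exposure, and nothing in the documents says how far the recurrence association is confounded.

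**Conclusion.** The point holds for recurrence only. A primary outcome with a directional hypothesis and a quoted between-arm power has no written between-arm analysis; the one analysis specified uses an exposure variable that regimen only partly determines. Regimen accounts for about 34-38% of log-AUC variance within a stratum on the planning CV and about 20% on the Table 1 spread, leaving about 62-80% not randomised.

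These shares assume log-normal AUC, 1:1 allocation, the full 1.7-fold effect, and an exposure measure that reflects the whole course. If dose/(CL/F) uses a single dose, regimen's share would be smaller. The conclusion itself rests on the text of Sections 9.2.1, 9.5.1 and 9.5.2 and not on these figures. The omission should be corrected before outcome data are analysed.

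**What to change.** Add one paragraph to Section 9.5.2 stating that:

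- the primary analysis of recurrence by Day 42 compares the randomised regimens, by a Cox model with regimen as the term or by a Kaplan-Meier risk difference;
- it is done separately in HIV-infected and HIV-uninfected children, to answer hypotheses 1 and 3;
- it includes all randomised episodes, not only PK-evaluable ones, and says how early treatment failures and losses to follow-up are counted;
- it uses the child-clustered robust variance already planned;
- its alpha is stated. For 47% against 27% with 80 per arm, power is 75.0% at 0.05, 65.1% at 0.025 and 59.1% at 0.05/3, so the choice matters.

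Keep the exposure-response Cox and PK/PD models as supporting analyses. In the same edit, define the dose in dose/(CL/F), and align the outcome window in Section 9.5.2 (day 28-42) with Section 9.2.1 (by day 42).

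The cost is one paragraph. Sections 6.4.1 and 6.4.2 already schedule follow-up to Day 42 for both regimens, so no new data are needed.

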### MALARIA CASE DEFINITION:

Uncomplicated malaria (all of the following)

- Fever (> 38.0°C tympanic) or history of fever in the previous 24 hours
  - Positive thick blood smear
  - Absence of complicated malaria
- Complicated malaria (any of the following)
- Evidence of severe malaria and parasitemia
  - Danger signs present and parasitemia
  - Parasite density > 500,000/μl

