### 6.3 Classification of Uncomplicated Malaria

All episodes of malaria will be classified as uncomplicated or complicated based on the following criteria:

Uncomplicated malaria (all the following must be present)

- 1) Fever ( $> 38.0^{\circ}\text{C}$  tympanic) or history of fever in the previous 24 hours
- 2) Positive thick blood smear
- 3) Absence of complicated malaria

Complicated malaria (any of the following)

- 1) Evidence of severe malaria (Appendix D) and parasitemia
- 2) Danger signs present and parasitemia
- 3) Parasite density  $> 500,000/\mu$ L

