#### **6.4.6 Criteria and management of Early/Late Treatment Failure**

Treatment outcomes will be based on 42-day treatment outcomes as per standard WHO classification system. Interim 28-day outcomes will also be assessed. The following criteria will be used for all participants participating in intensive and/or population PK studies. Patients treated for uncomplicated malaria but classified as early or late clinical failures within 14 days of treatment will be treated with quinine. Clinical failures between days 15-42 will be treated as a new episode of malaria.

##### Early Treatment Failure: Study Days 0, 1, 2, and 3

- Development of danger signs or severe malaria on study Days 0-3 in the presence of parasitemia
- Parasitemia on study Day 2 higher than on Day 0, irrespective of temperature
- Parasitemia on study Day 3 with temperature > 38.0° C (tympanic)
- Parasitemia on study Day 3 > 25% of count on Day 0

##### LPF (Late Parasitological Failure): Days 4 to 42

- Presence of parasitemia on Days 4-42 with temperature < 38.0 ° C (tympanic) and no history of fever in past 24 hours, without previously meeting any of the criteria for early treatment failure

##### LCF (Late Clinical Failure): Days 4 to 42

- Development of danger signs or severe malaria Days 4 to 42 in the presence of parasitemia, without previously meeting any of the criteria of early treatment failure or late parasitological failure
- Temperature > 38.0 ° C (tympanic) or history of fever in past 24 hours on Days 4 to 42 in the presence of parasitemia, without previously meeting any of the criteria of early treatment failure or late parasitological failure

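### The primary recurrence event differs between 9.2.1 (recurrent malaria) and 9.5.2 (recurrent infection under WHO outcomes), so the status of afebrile parasitaemia and the Cox event date are not settled

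*Combined protocol and SAP*

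**What the plan says.** Section 9.2.1 gives the second primary outcome as "Recurrent malaria following treatment by day 42 (recrudescence or new infection". Section 9.5.2 relates drug exposure, by Cox models, to the "primary treatment outcome (recurrent infection at day 28-42 using standard WHO treatment outcomes". It makes only sub-patent infection found by LAMP a secondary outcome.

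The case definition in the trial schema and in 6.3 is conjunctive: "Uncomplicated malaria (all the following must be present". One required element is measured fever or "history of fever in the previous 24 hours". Complicated malaria needs severe features, danger signs or a density above 500,000/µL, each with parasitaemia.

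Section 6.4.6 sets the WHO categories. "Treatment outcomes will be based on 42-day treatment outcomes as per standard WHO classification system", and "Interim 28-day outcomes will also be assessed". LPF is parasitaemia on Days 4 to 42 with temperature below 38.0 °C and "no history of fever in past 24 hours, without previously meeting any of the criteria for early treatment failure". Late clinical failure (LCF) on Days 4 to 42 applies only "without previously meeting any of the criteria of early treatment failure or late parasitological failure".

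Appendix E repeats the categories with two differences. Its febrile LCF bullet stops at Day 28, although the heading above it runs to Day 42. Its definition of adequate clinical and parasitological response (ACPR) excludes anyone who earlier met a failure criterion. The ACPR text in 6.4.6 has no such exclusion and names only the 6-dose regimen, although 5.1 gives one arm 10 doses.

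**The concern.** Recurrence is a primary outcome, the event in the exposure-outcome Cox models, and the basis of the power statement in 9.5.1. Under the protocol's own definitions, the malaria term in 9.2.1 and the infection and WHO-outcome terms in 9.5.2 cover different sets of children and can give different event dates. No section says which governs.

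The choice also affects how objective the event is. At scheduled visits, an event that includes LPF rests on a smear read by laboratory staff outside patient care (6.8). An event that requires fever can turn on a reported history, in a trial that the schema describes as open-label. Left unstated, the event could be chosen after the data are seen.

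**Working it through.** **The plan's own figure.** Section 9.5.1 cites a 42-day recurrence of 47% on efavirenz-based ART and claims 80% power for a 20% difference. Inputs: 80 per arm (HIV-infected, 9.5.1), and the difference read as 20 points, 47% v 27%. The plan gives no alpha or sidedness for recurrence, so 0.05 is my assumption.

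- Pooled standard error: √(2 × 0.37 × 0.63 / 80) = 0.0763
- Unpooled standard error: √((0.47 × 0.53 + 0.27 × 0.73) / 80) = 0.0747
- Two-sided: (0.20 − 1.960 × 0.0763) / 0.0747 = 0.675, power 75.0%
- One-sided: (0.20 − 1.645 × 0.0763) / 0.0747 = 0.997, power 84.1%
- One-sided with continuity correction: 81 per arm for 80% power, the closest match to the plan

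The claim can be approximately reproduced, and this point does not depend on it. What matters here is that 9.5.1 does not say which event the 47% counts.

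**The two event definitions side by side.** These are example patterns with no severe or danger signs and density not above 500,000/µL. No rates are assumed, and the 28-42 range is taken as the interim and final assessments.

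| Pattern | 9.2.1 with the case definition | 9.5.2 with 6.4.6 |
|---|---|---|
| First parasitaemia Day 35, febrile | Event, Day 35 | Event (LCF), Day 35 |
| Febrile parasitaemia Day 21 | Event, Day 21 | Event (LCF), Day 21 |
| Afebrile parasitaemia Day 35, never febrile | No event | Event (LPF), Day 35 |
| Afebrile parasitaemia Day 21, febrile parasitaemia Day 28 | Event, Day 28 | Event (LPF), Day 21; LCF then barred |

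The third pattern changes event status. The fourth moves the event time by 28 − 21 = 7 days. Neither depends on how the 28-42 range is read.

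**The two classification texts.**

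- Febrile parasitaemia on Day 35 without danger signs is LCF in 6.4.6. In Appendix E it is past the bullet's Day 28 limit, and it cannot be LPF because the child is febrile.
- Section 6.4.6 states what follows a clinical failure and is silent on LPF. A child with LPF on Day 21 who receives no further treatment and is smear-negative on Day 42 meets the LPF criterion, yet also fits the 6.4.6 ACPR wording. Appendix E excludes that child from ACPR.
- Read literally, the 6.4.6 ACPR wording does not describe the 10-dose arm.

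**Related wording.** Secondary objective 6 (2.2) refers to recurrent malaria; its outcome (9.2.2, item 6) refers to treatment failure.

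**The case against.** The strongest reply is that these are loose synonyms rather than rival endpoints. Section 9.2.1 does not cite the case definition, its parenthesis speaks of recrudescence or new infection, and 6.7 and 9.5.1 move freely between repeat infection, reinfection and recurrence. That stands in part: that 9.2.1 leaves out LPF is an inference from the case definition, not a stated rule. But the parenthesis describes where the parasites came from and does not remove the fever criterion. If the terms are meant to be equivalent, one sentence would say so.

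A reader might infer from 9.5.2 that recurrences before Day 28 are discarded. The documents do not support that. Section 6.4.6 has an interim Day 28 and a final Day 42 assessment, which probably explains the range, and the literal reading would contradict the Day 4 to 42 categories that 9.5.2 itself invokes. The phrase needs rewording but is not evidence of a truncated window.

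A reader might also infer that the clock is undefined. It is not: 5.1.1 makes the first treatment day Day 0 and uses study days throughout. Early failure is partly covered, since it is defined in 6.4.6 and PK sampling stops under 6.4.6 and 6.7.1, but its entry into the Cox model is not stated.

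The event behind the 47% may be defined in the cited study, which I have not seen. The Appendix E and ACPR points may be drafting slips. They still misclassify children if followed as written, although 6.4.6 applies its own criteria to all participants and nothing makes Appendix E the scoring rule.

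**Conclusion.** The point holds as a conflict of definition and should be fixed before analysis. Confidence is high that the text leaves two things open: whether LPF is a primary recurrence event, and which date applies when LPF is followed by fever. The conflicts in the LCF window and in ACPR are explicit in the text.

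No size of bias is claimed. A reader might want to turn the conflict into lost events or lost power, but the documents give neither the share of recurrences that are LPF nor their timing. The conclusion rests on one assumption: that malaria in 9.2.1 carries the meaning of the protocol's own case definition.

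**What to change.** All changes concern outcome classification; none alters a treatment rule.

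1. Use one event in 9.2.1 and 9.5.2. The text of 9.5.2 with 6.4.6 supports the first microscopy-detected late failure (LPF or LCF) on Days 4 to 42, timed from Day 0 and dated at the first qualifying smear. Make febrile recurrent malaria a sensitivity analysis only.
2. State how early treatment failures on Days 0 to 3 enter the Cox model.
3. In 9.5.2, replace the day 28-42 phrase with: by Day 42 (interim Day 28).
4. Make the febrile LCF bullet in Appendix E match its own heading and 6.4.6.
5. In the 6.4.6 ACPR definition, refer to the assigned regimen and add Appendix E's exclusion of earlier failures.
6. State in 9.5.1 which event the 47% and the 20% difference refer to.
7. Use one term in secondary objective 6 and its outcome.

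The cost is wording in 2.2 (and its copy in the schema), 6.4.6, 9.2.1, 9.2.2, 9.5.1, 9.5.2 and Appendix E. No new data or visits are needed.
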